5.2 Manner in Which Risks will be Minimized

This study minimizes risks to participating patients in the following ways:

- Study subjects will be under regular supervision by trained clinical personnel specifically to monitor temperature, as well as to monitor for adverse events and changes in hemodynamic parameters throughout the study period, in addition to normal critical care nursing staff.
- Changes in subject temperature happen over relatively long periods of time, usually over the course of hours (not seconds or minutes). As such, if the CoolStat is not able to cool or hold desired temperature ranges, alternative cooling therapies are available and can be applied in relatively short order.
- High and low monitoring alarms for the subjects will be set as follows:
 - The subject's core temperature (either esophageal, SpotOn, or bladder) will be continuously monitored and recorded in the CRFs, with procedures to stop the CoolStat if the core temperature is $<36^{\circ}\text{C}$ for a sustained period of 5 minutes, to limit the potential to overcool the subject. Subjects must have a core temperature of $<39.5^{\circ}\text{C}$ at the start of the cooling treatment. If subjects have a temperature $>39.0^{\circ}\text{C}$ for over 4 hours, CoolStat treatment will be stopped and an alternative method of cooling will be initiated. Likewise, the CoolStat will be stopped if the subject has a sustained core temp $> 39.5^{\circ}\text{C}$ sustained for 5 minutes.
 - The subject's tympanic temperature will also be continuously monitored by the hospital's normal monitoring system and manually monitored and recorded in the CRFs. The tympanic temperature will alarm in the hospital's monitoring system if the tympanic temperature drops to $<34^{\circ}\text{C}$, to limit the potential to overcool the subject's brain. Additionally, tympanic temperature will also alarm if the tympanic goes $>39^{\circ}\text{C}$, to limit the potential that the subject temperature gets too high. If the temperature is observed $<34^{\circ}\text{C}$ for a sustained period of at least 5 minutes, or $>39^{\circ}\text{C}$ for over 4 hours, use of COOLSTAT device will be discontinued on that subject. Likewise, the CoolStat will be stopped if the subject has a sustained tympanic temp $> 39.5^{\circ}\text{C}$ sustained for 5 minutes.

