9.2 Phase 0 – Monitoring Before Cooling

1. Prior to starting the COOLSTAT device, clinical personnel will confirm that the subject is intubated and mechanically ventilated.
2. The COOLSTAT device shall be brought into the subject's room and the core temperature sensor (either esophageal - Smiths Medical Esophageal Stethoscope Temperature Sensor; Series 400. Model ES 400-12 - or bladder - Foley Catheters, BARDEX® I.C., Temperature-Sensing, Dual Connector 5 mL balloon, 16 French - or 3M Spot On™ Temperature Monitoring System) will be plugged into the COOLSTAT device. The subject's core temperature should be confirmed at this time to be $\geq 38.3^{\circ}\text{C}$, but $<39.5^{\circ}\text{C}$, as displayed on the CoolStat device.
3. Delivery of any medications or other fluids orally will be recorded on the CRF due to potential temporary effect on esophageal temperature probe. Even room temperature fluids may affect the temperature reading, and time of administration should be recorded.
4. A tympanic temperature sensor will be placed in the subject's ear and connected to the hospital's temperature monitoring system to record temperature. The acceptable tympanic temperature range is 34 to 39°C, and the hospital system temperature alarms will be set to indicate any readings outside that range. NOTE – in this study, tympanic

temperature is only considered as a surrogate for brain temperature for safety monitoring. Either esophageal or bladder temperature will be used as core temperature. It can take about 5 to 10 minutes for the tympanic temperature sensor to reach a steady state monitoring condition when initially placed in the subject's ear.

- 5. The COOLSTAT device will be prepared and the set up initiated, but not turned on. COOLSTAT set up and operation procedures are provided in the Operator's Manual, as well as a Quick Start Guide.
- 6. The subject target temperature will be set to 36.5 °C on the CoolStat device.
- 7. The subject's core temperature will be monitored and recorded in the CRFs, from the esophageal, SpotOn, or bladder temperature sensor. The acceptable core temperature range is 36°C to 39°C. The patient may remain >39.0 °C but <39.5 °C for up to 4 hours, at which point the CoolStat treatment will be discontinued and an alternative cooling method initiated. Likewise, the CoolStat will be stopped if the subject has a sustained core temp > 39.5 C sustained for 5 minutes.

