9.3 Phase 1 – Active Cooling Phase

Subjects will receive COOLSTAT cooling treatment, with a maximum of 30 cmH₂O of air pressure (as automatically controlled by the device). The COOLSTAT will be operated in closed-loop control mode and will automatically modulate and control air flow and maintain the subject's core temperature between 36 °C and 37.5 °C, as measured by the esophageal, SpotOn, or bladder temperature sensor. The device will be set to target 36.5 °C.

The COOLSTAT will attempt to cool to and maintain this temperature range over the phase period. The core temperature will be recorded automatically by the COOLSTAT device, and is displayed on the COOLSTAT screen.

While the COOLSTAT is in use, no other cooling therapies will be used other than antipyretics.

Throughout Phase 1, the subject's temperature and vital signs will be monitored per NCCU protocol, as well as data collected in the CRFs. If any alarms occur, the appropriate action will be taken as described herein. COOLSTAT device errors will be addressed via an available trained technician and study team training (See Operator's Manual for a description of the possible device errors). Treatment may be discontinued at any time if adverse events are encountered or alternate cooling methods are required on an urgent basis. The Investigator or their designee must review any such emergency changes to therapy and complete an Adverse Event form detailing the reason for the change.

Per standard of care in the NCCU, maximum allowed limits will be imposed for a sustained increase in SBP >5 minutes above existing SBP threshold limits (specific to the indication being treated) despite standard of care intervention. In this event, COOLSTAT use will be discontinued for that subject. Once the COOLSTAT is discontinued due to SBP elevation, it will not be restarted for that subject. However, the study team will continue to monitor SBP to see if it recovers back to baseline value after the COOLSTAT is turned off. The Investigator or their designee must complete an Adverse Event form detailing the event and the value of the SBP prior to, during and after the COOLSTAT was used.

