Similarly, per standard of care in the NCCU, a maximum allowed limit will be imposed for a sustained increase in ICP >5 minutes above max threshold despite standard of care intervention (using existing max institutional limits for the indication being treated). In this event, COOLSTAT use will be discontinued for that subject. Once the COOLSTAT is discontinued due to ICP elevation, it will not be restarted for that subject. However, the study team will continue to monitor ICP to see if it recovers back to baseline value after the COOLSTAT is turned off. The Investigator or their designee must complete an Adverse Event form detailing the event and the value of the ICP prior to, during and after the COOLSTAT was used. See Section 10.0 on procedures following the occurrence of an Adverse Event.

The Investigator or their designee will perform an initial cooling assessment 4 hours after COOLSTAT cooling has begun to determine if the subject has reached normothermia (≤ 37.5 C) sometime within the 4-hour cooling period. Starting from the initiation of normothermia, a subject's core temperature may fluctuate (within about 36.0-37.5 C), but

Transnasal Induction of Normotherapy in NCCU Fever Patients

if the core temperature $>39.0^{\circ}\text{C}$ for 4 hours, CoolStat treatment will be stopped and the subject will be switched to an alternative cooling method. If normothermia ($\leq 37.5^{\circ}\text{C}$) is not achieved within the 4-hour period, the Investigator or their designee will remove the subject from the COOLSTAT device. The subject will be classified as a treatment failure and placed on standard of care treatment at the discretion of the Investigator or their designee and manual data collection will continue per the instructions for Phase 2 in Section 9.4. NOTE – if the Investigator feels that the subject's temperature is approaching the target and the subject is being adequately cooled, CoolStat device operation can be allowed to continue beyond the 4-hour period. The Investigator should note if this is the case in the CRF.

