If a subject must be disconnected from the CoolStat device for transport from the NCCU to another unit (e.g., to radiology or angiography suite), they will be reconnected to the device at steady state if their core temperature upon being reconnected to the CoolStat is $\leq 37.5^{\circ}\text{C}$. If the subject's temperature is $> 37.5^{\circ}\text{C}$ upon being reconnected to the device, the device will be given up to an additional 4 hour-period to bring the patient to normothermia ($\leq 37.5^{\circ}\text{C}$). Once the subject's core temperature is $\leq 37.5^{\circ}\text{C}$, the device will be considered in steady state. Only the total steady state time will be used for analysis. Subjects who are disconnected from the CoolStat for transport may be given a bolus of cold saline before transport. This will be determined by the clinical provider a case-by-case basis.

The COOLSTAT does not have a re-warming function. If the subject's core temperature drops below 36°C , warming therapies can be initiated at the discretion of the Investigator or the attending clinician(s). The subject can stay on the COOLSTAT and continue with the study as long as core temperature can be adequately controlled at the discretion of the Investigator or the attending clinician(s). Any change to therapy must be recorded in the case report form. COOLSTAT therapy will be discontinued if tympanic temperature drops below 34°C for a sustained period of at least 5 minutes.

The CoolStat nasal mask will be removed at least every 4 hours to inspect nasal tissue for the development of any pressure sores. Petroleum gel may be applied to facilitate a strong seal below the nasal mask pillows and the nostrils without requiring much pressure from the mask straps.

The COOLSTAT therapy will be discontinued at the end of Phase 1, at which point the subject can be placed on alternate cooling therapies at the discretion of the attending clinician.

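### The 5-minute stop for core temperature below 36°C in 5.2 is not carried into 9.2 or 9.3, and 9.3 lets such a subject stay on the device with no core time limit

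*Combined protocol and SAP*

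**What the plan says.** Section 5.2 lists the safeguards against overcooling. Core temperature is monitored continuously, "with procedures to stop the CoolStat if the core temperature is" below 36°C for a sustained 5 minutes. The same section has high-side core stops (above 39.0°C for over 4 hours, above 39.5°C for 5 minutes) and a tympanic stop (below 34°C for at least 5 minutes).

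Section 9.2, item 7, states: "The acceptable core temperature range is 36°C to 39°C". It then gives actions for the upper end only.

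Section 9.3 governs active cooling. Below 36°C, it says, warming may be started at discretion, and "The subject can stay on the COOLSTAT and continue with the study as long as core temperature can be adequately controlled", again at discretion. The low-temperature discontinuation it states is the tympanic one: "COOLSTAT therapy will be discontinued if tympanic temperature drops below" 34°C for at least 5 minutes. It also says: "If any alarms occur, the appropriate action will be taken as described herein".

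On restarting, 9.3 is explicit for blood pressure ("Once the COOLSTAT is discontinued due to SBP elevation, it will not be restarted for that subject") and for intracranial pressure ("Once the COOLSTAT is discontinued due to ICP elevation, it will not be restarted for that subject"). It has a reconnection rule for transport. It has no restart rule for a low-core stop.

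On analysis, the Statistical Methodology row of 1.0 bases maintenance on subjects who reach normothermia by 4 hours and go on with cooling. Section 13.0 names treatment-initiated and treatment-completed populations. Neither mentions a subject stopped for low core temperature.

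**The concern.** Two current sections give different instructions for the same event. Bedside staff work from section 9, and the section 9 text on core below 36°C permits what 5.2 says will be stopped. One clinician may stop at 5 minutes; another may warm the subject and continue. Section 14.15 allows no deviations, yet following 9.3 past 5 minutes departs from 5.2.

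The 36°C limit also carries weight elsewhere. In 5.1.1 the expected brain temperature is worked out from it: about 1°C lower gives roughly 35°C, and about 3°C lower, as in the pig model, gives roughly 33°C. Over-cooling and induced brain hypothermia are both anticipated adverse events in 10.4, and 9.3 notes that the device cannot re-warm.

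The secondary stake is the maintenance endpoint. Permanent removal for overcooling is a failure to hold temperature in the band. If such a subject leaves the denominator, the reported proportion does not show that failure.

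**Working it through.** The plan gives no figure for how often core falls below 36°C, so there is none to reproduce. The main check is a comparison of text.

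**Step 1. Triggers and actions side by side.**

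| Trigger | 5.2 | 9.2 | 9.3 |
|---|---|---|---|
| Core >39.0°C, 4 h | stop | stop | stop |
| Core >39.5°C, 5 min | stop | stop | not repeated |
| Core <36°C, 5 min | stop | lower end of range, no action | may warm, may stay on, no time limit |
| Tympanic <34°C, 5 min | discontinue | alarm range only | discontinue |
| SBP or ICP above limit, >5 min | discontinue | assessed before cooling | discontinue, no restart |

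The low-core row is the only one in which 9.3 permits something that 5.2 does not. The >39.5°C rule is missing from 9.3 too, but nothing there contradicts it.

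**Step 2. Apply both rules.** Take a subject whose core has been below 36°C for more than 5 minutes, with tympanic temperature above 34°C. Under 5.2 the device should already be stopped. Under 9.3 the subject may remain on it while control is judged adequate. The sentence about acting on alarms points to rules elsewhere, but does not say that it overrides this specific permission.

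**Step 3. Does the endpoint supply a limit instead?** Maintenance allows 20% of steady-state time out of band. Assume normothermia is first reached at hour 4, with no transport interruption:

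- 8-hour subject: 8 − 4 = 4 h; 0.20 × 4 h = 0.8 h = 48 min.
- 24-hour subject: 24 − 4 = 20 h; 0.20 × 20 h = 4 h.

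A subject could spend that long below 36°C, otherwise in band, and still meet the criterion. This is what the endpoint tolerates, not a forecast. It shows only that the endpoint does not replace the 5-minute rule.

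**Step 4. What the denominator changes.** Suppose all subjects reach normothermia within 4 hours, exactly one is permanently stopped for low core, and *s* of the others succeed on maintenance.

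- First 10 subjects: kept as a failure, *s*/10 ≥ 0.75 needs *s* = 8; excluded, *s*/9 ≥ 0.75 needs *s* = 7. At *s* = 7 these are 7/10 = 70.0% and 7/9 = 77.8%. Section 6.10 asks for 8 of 10. Read literally, 7 successes miss either way; read as the underlying 75%, exclusion passes and failure does not.
- Double nostril group, 20 subjects: kept as a failure needs *s* = 15 (15/20 = 75%); excluded also needs *s* = 15 (14/19 = 73.7%, 15/19 = 78.9%). One subject does not change the verdict.

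The scoring choice always moves the reported proportion. With one such subject it alters a decision only at the first-10 review, and only on one reading of the gate.

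**The case against.** The strongest reply is that the sections can be reconciled. Section 5.2 says use is discontinued for tympanic, SBP and ICP breaches, but only that the device is stopped for low core; 9.4 shows that the Start/Stop button leads to a pause mode. A pause with warming, the subject remaining in the study, fits both sections. Over-cooling is listed in 10.4, so the options in 10.3 (suspend airflow, switch method, remove) already apply. The target is 36.5°C with flow adjustable down to about zero (3.2), so a subject below 36°C is at least 0.5°C under target and should be receiving little airflow. The Operator's Manual, case report forms and IDE appendices are not among the documents and may hold the procedure.

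Much of this stands. The practical difference between stopping and staying on is probably small, and 10.3 does give discretionary actions. But the pause reading is not written: 9.3 neither requires airflow to stop nor sets a core duration, and 10.3 has no restart rule. A procedure in another document would leave the protocol inconsistent.

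A reader might infer two stronger things. One is that subjects have no protection against overcooling; the tympanic stop in 9.3 and closed-loop control contradict that. The other is that a subject removed for overcooling would count as a maintenance success on a short record. The documents do not support this either: given the restriction in 1.0 to subjects who continue cooling, exclusion is the more natural reading.

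**Conclusion.** The inconsistency is real and should be corrected. Section 5.2 states a 5-minute low-core stop, 9.2 and 9.3 do not carry it, and 9.3 permits the opposite. It concerns the core back-up rule, not the whole brain-temperature margin.

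The scoring point is secondary. A permanently stopped subject could leave the maintenance denominator, because 1.0 restricts the population and 13.0 is silent on such a subject. No size is claimed for the effect on safety or on the result: the documents give no overcooling rate, and the counts in step 4 are conditional on one such subject occurring. The conclusion rests on the protocol text alone and would be milder if an unseen operating document already carries the stop.

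**What to change.** In 9.2 (item 7) and 9.3, state that CoolStat airflow is stopped if core temperature is below 36°C for a sustained 5 minutes. Limit warming with continued cooling to shorter dips. Say whether cooling may restart once core is back in range, as 9.3 already does for SBP and ICP.

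In 13.0, state that a subject permanently stopped for core below 36°C stays in the maintenance denominator and counts as a failure. Apply the same rule to the 8-of-10 criterion in 6.10, and align the population wording in 1.0.

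The cost is a few sentences and, under 14.15, FDA approval of the amendment. No new measurements or subjects are needed: the device records core temperature every second (12.6), and 9.3 already requires therapy changes on the case report form. The downside is that the maintenance proportion may be slightly lower.

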5.3 Justification for the Investigation

This study will evaluate the performance and safety in a limited number of subjects who require cooling therapy to normothermia and who will be closely monitored in an intensive care setting. The feasibility and safety of using dry nasal air as a means of cooling subjects was previously evaluated with both non-febrile and febrile subjects using a surrogate device (CPAP) [8, 28]. This study shall demonstrate the performance of the COOLSTAT Transnasal Thermal Regulating Device under controlled conditions in febrile subjects.

5.4 Description of Patient Population

Details concerning the included patient population are provided in Section 8.0.

5.5 Alternative to this Treatment

Currently, the first-line method to cool a febrile patient is administering antipyretics. Patients who continue to be febrile and are clinically indicated for cooling are often prescribed more aggressive target temperature management (TTM) methods using

surface or intravascular systems for restoring normothermia. Multiple means of cooling febrile patients, including usage of ice packs and ice water, surface cooling devices, and catheter cooling devices are commonly available [3]. Examples of surface cooling devices include the CSZ Blanketrol and Arctic Sun Temperature Management System; examples of endovascular cooling devices include the Reprieve Endovascular Temperature Therapy System and Cool Line system [6].

5.5.1 Advantages of COOLSTAT Compared to Predicate Technologies

The primary anticipated benefits of COOLSTAT when compared with alternative TTM methods are:

- it can cool to and maintain normothermia with a simple nasal mask on the patient's nose with minimal disruption to patient care,
- it is portable and has an internal battery that will allow for continued cooling during short transport periods within the hospital (for miscellaneous short procedures),
- it is relatively small and portable with mounting options on an IV pole or sitting next to the patient's bed,
- it does not require cold storage of fluids or ice,
- it does not require the insertion of an invasive catheter,
- it has the potential to be used earlier than predicate treatments since it is quick and easy to setup,
- it is easy to use for long periods of time, needing minimal clinician interaction after setup, and
- it is expected to reduce the incidence of shivering response when compared to surface cooling methods since the cooling method is from the inside out, which may not trigger temperature sensors located in the skin² [6, 13].

5.5.2 Risks and Disadvantages of COOLSTAT Compared to Predicate Technologies

Analytical modelling and prior studies have determined that the rate of energy removal, and hence the rate of patient cooling using transnasal cooling provided by COOLSTAT, is somewhere in the mid-range of cooling rates of alternative TTM systems for induced normothermia [2, 3, 4, 12]. Endovascular cooling has the ability to hold a targeted temperature with a high degree of stability [3, 6]. The COOLSTAT is not expected to be as precise, but should still hold temperature within the normothermic range of 36°C – 37.5°C, according to analytical models and as demonstrated in 24-hour pig tests.

² Skin temperature receptors contribute to about 20% of the shivering response [13].

6.0 Study Design

6.1 Definitions

AE	Adverse Event
CRF	Case Report Form
GCP	Good Clinical Practice
ISO	The International Organization for Standardization
NCCU	Neurosciences Critical Care Unit
PI	Principal Investigator
SOP	Standard Operating Procedure

6.2 Purpose and Objectives

The objective of this study is to evaluate safety and performance of the COOLSTAT® Transnasal Thermal Regulating Device in reducing temperature in a population of febrile subjects who meet the inclusion/exclusion criteria. Results of this study will provide information about the safety and functionality of the COOLSTAT device in a clinical setting to cool to and maintain subjects at normothermic temperature.

6.3 Primary Efficacy Endpoint and Success Criteria

This feasibility study should confirm that the COOLSTAT system has the ability to safely and adequately achieve and maintain normothermic cooling therapy with its control system over a specified period for subjects who were enrolled in the study.

This cooling aspect of the trial will be considered a success if at least 75% of the subjects achieve the following criteria:

- Cooling Performance: The subjects reach normothermia (core temperature $\leq 37.5^{\circ}\text{C}$) within 4 hours of starting COOLSTAT cooling.
- Temperature Maintenance: The subjects are held within a 1.5°C temperature band, between $36^{\circ}\text{C} - 37.5^{\circ}\text{C}$, for 80% of the steady state time following the initial achievement of 37.5°C .³

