6.6 Sample size calculations

The sample size was determined from the calculation below, using the following assumptions:

$$n = \left[\frac{z_{\alpha} \sqrt{p_0(1-p_0)} + z_{\beta} \sqrt{p_1(1-p_1)}}{p_1 - p_0} \right]^2$$

n: minimum sample size

$p_0 = 0.9$ Assumed proportion of subjects successfully cooled

$p_1 = 0.75$ Lowest acceptable proportion of subjects successfully cooled

$\delta = |p_1 - p_0| = 0.15$ Difference between ideal and minimum acceptable

Confidence (α): 90%

$$z_{95} = 1.28$$

Statistical Power (β): 80%

$$z_{80} = 0.84$$

n = 25 subjects completing treatment, therefore a sample size of 30 subjects was selected to allow for dropouts. The study will enroll up to 70 subjects, accounting for a 55% expected post-consent screen failure rate. Enrollment will stop once the 30th subject receives COOLSTAT therapy.

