13.0 Statistical Analysis Plan

The primary efficacy analysis for cooling performance will be based on the evaluable populations of subjects who undergo cooling treatment with the COOLSTAT System. Analysis will be performed on treatment initiated and treatment completed populations. Subjects who achieve normothermia (core temperature $\leq 37.5^{\circ}\text{C}$) within 4 hours of starting COOLSTAT treatment and maintain normothermia for the duration of the treatment will be determined to have been treated successfully.

The primary efficacy analysis for temperature maintenance will be based on the evaluable population of subjects who maintain normothermia (core temperature between 36°C and 37.5°C) for at least 80% of the time following the initial achievement of 37°C will be determined to have been treated successfully.

The proportion of subjects fulfilling success criteria and 90% confidence intervals will be reported and compared to the a priori minimum acceptable criteria:

- at least 75% of the subjects will reach normothermia (core temperature $\leq 37.5^{\circ}\text{C}$) within 4 hours of starting COOLSTAT cooling, and
- at least 75% of the subjects' core temperatures remain between 36°C and 37.5°C for 80% of the steady state time following the initial achievement of 37.5°C .

Continuous measurements will be summarized using the mean and standard deviation. Categorical variables will be reported using percentages and confidence intervals. Data collected will be plotted to demonstrate the change in core temperature from baseline.

An exploratory analysis of participant subgroups will be performed, stratified by stroke presentation (ischemic versus hemorrhagic). Cooling performance and AEs will be evaluated by subgroup.

Double nostril air flow and single nostril air flow subjects will not be merged or directly compared. The results from subjects treated with single nostril flow will be analyzed separately from subjects treated with double nostril air flow.

Subjects 1 through 20 will be assigned to the double nostril air flow treatment group:

- Subjects 1 through 10 will be treated for 8 hours (N=10)
- Subjects 11 through 20 will be treated for 24 hours (N=10)

Subjects 21 through 30 will be assigned to the single nostril air flow treatment group

- Subjects 21 through 30 will be treated for 24 hours (N=10).
- Subjects 21 through 30 will be treated using a dose escalation model:
 - Dosing for this cohort (flow rate) will begin at 30 LPM.

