 - The dose will be increased by 10 LPM if 3 consecutive subjects complete the study protocol with no serious adverse events (as listed in section 10.5) or unanticipated adverse device events.
 - Up to three doses will be evaluated in this cohort (30 LPM, 40 LPM, 50 LPM).
- The purpose of this cohort is to assess the safety of and optimal dose for the single nostril air flow configuration of the CoolStat.
- Each subject will be examined for adverse events, serious adverse events, and unanticipated adverse device events by an intensivist or otolaryngologist within 24 hours of completing CoolStat therapy.
- Each flow rate cohort must be evaluated by an intensivist or otolaryngologist prior to advancing the protocol to the next increased flow rate cohort.

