13.1 Primary Performance Outcome Analysis

The primary hypothesis regarding cooling performance is that at least 75% of the subjects will reach normothermia (core temperature $\leq 37.5^{\circ}\text{C}$) within 4 hours of starting COOLSTAT cooling.

The primary hypothesis regarding temperature maintenance is that at least 75% of the subjects' core temperatures remain between 36 °C and 37.5 °C for 80% of the steady state time following the initial achievement of 37.5 C.

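### The 90% confidence and 80% power in 6.6 belong neither to the success rule in 6.3 nor to the separate groups of 20 and 10 that will be analysed

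*Combined protocol and SAP*

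**What the plan says.** **Success rule.** Section 6.3 states: "This cooling aspect of the trial will be considered a success if at least 75% of the subjects achieve the following criteria". It then lists two criteria: normothermia within 4 hours, and temperature held in the band for 80% of steady state time. No test or confidence limit is attached. Section 6.10 applies the 75% endpoint as a count, 8 of the first 10 subjects, for each criterion in turn.

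**Sample size.** Section 6.6 uses a one-sample formula with an assumed success proportion of 0.90 and 0.75 as the "Lowest acceptable proportion of subjects successfully cooled". It gives 90% confidence (z = 1.28) and 80% power (z = 0.84), and concludes: "n = 25 subjects completing treatment, therefore a sample size of 30 subjects was selected to allow for dropouts".

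**Analysis.** Section 13.0 and the summary (1.0, Statistical Methodology) say the proportions and "90% confidence intervals will be reported and compared to the a priori minimum acceptable criteria". Sidedness, method and deciding limit are not given.

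**Groups.** Section 13.0 also says: "Double nostril air flow and single nostril air flow subjects will not be merged or directly compared". Subjects 1 to 20 form the double nostril group and 21 to 30 the single nostril group. Of the latter it says: "The purpose of this cohort is to assess the safety of and optimal dose for the single nostril air flow configuration".

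**Hypotheses.** Section 13.1 states one for each criterion, the first being: "The primary hypothesis regarding cooling performance is that at least 75% of the subjects will reach normothermia".

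**The concern.** A reader of 6.6 would take the final result to carry 90% confidence and 80% power. Those properties attach to a particular test at a particular size. The plan describes no such test, and no group of 25 or 30 will be analysed.

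The role of the interval is also open. A result can meet 6.3 while its interval extends far below 75%, and the text does not say what the comparison with 75% is for.

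The thing that must reach 75% is not defined in one way either:

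- The summary (Hypothesis and Statistical Methodology), 6.10, 13.1 and the bullets in 13.0 give two separate proportions.
- Section 6.3 can be read as one proportion of subjects who meet both criteria.
- The first paragraph of 13.0 is stricter, with no 80% allowance: subjects who reach normothermia in 4 hours and "maintain normothermia for the duration of the treatment will be determined to have been treated successfully".
- The second paragraph of 13.0 counts time from first reaching 37 °C, where the other statements use 37.5 °C.

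If these points are settled only after the counts are known, the choice of rule could be influenced by the data.

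**Working it through.** **1. The plan's own figure.** Inputs from 6.6: 0.90, 0.75, z = 1.28, z = 0.84, difference 0.15.

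n = [(1.28 × √(0.9 × 0.1) + 0.84 × √(0.75 × 0.25)) / 0.15]² = [(0.3840 + 0.3637) / 0.15]² = 24.85, rounded up to 25. It reproduces. The value 1.28 is the one-sided 90% quantile.

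**2. The 6.3 rule, one criterion.** Pass if the observed proportion is at least 75%, so the chance of passing is P(X ≥ k) for X ~ Binomial(n, p), with k the smallest count reaching 75%.

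| n | k | true 70% | true 75% | true 90% |
|---|---|---|---|---|
| 10 | 8 | 38.3% | 52.6% | 93.0% |
| 20 | 15 | 41.6% | 61.7% | 98.9% |
| 25 | 19 | 34.1% | 56.1% | 99.1% |
| 30 | 23 | 28.1% | 51.4% | 99.2% |

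No row corresponds to 90% confidence with 80% power.

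**3. A lower-limit rule instead.** Suppose an exact (Clopper-Pearson) lower limit had to exceed 75%. Alpha is the pass probability at 75%, power that at 90%.

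| n | limit | count needed | alpha | power |
|---|---|---|---|---|
| 20 | one-sided 90% | 18 | 9.1% | 67.7% |
| 20 | two-sided 90% | 19 | 2.4% | 39.2% |
| 10 | one-sided 90% | 10 | 5.6% | 34.9% |
| 10 | two-sided 90% | none (10/10 gives 74.1%) | – | – |
| 30 pooled | one-sided 90% | 26 | 9.8% | 82.5% |

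Only the pooled 30, all evaluable, would reach 80%, and 13.0 rules out pooling.

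**4. The formula as laid out, with 0.90 as the null.** The exact one-sided 10% test at n = 20 rejects at 15 or fewer, with power 58.5% at a true 75%. At n = 10 it rejects at 7 or fewer, with power 47.4%. The stated 80% is not met here either.

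**5. Where the interval and the rule part.** 15/20 meets 6.3, and its exact two-sided 90% interval is 54.4% to 89.6%. 18/20 has a lower limit of 71.7% two-sided and 75.5% one-sided, on opposite sides of 75%.

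**6. Separate or composite.** At n = 20, assume equal rates p for the two criteria, independence, and all 20 subjects in both denominators. Separate: P(X ≥ 15 | 20, p)². Composite: P(X ≥ 15 | 20, p²).

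| p | separate | composite |
|---|---|---|
| 75% | 0.617² = 38.1% | p² = 0.5625: 6.9% |
| 90% | 0.989² = 97.8% | p² = 0.81: 83.6% |

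If exactly the same subjects meet both criteria, the two readings coincide (61.7% at 75%). The documents give no joint rate, so these figures only illustrate.

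**The case against.** The study calls itself a feasibility study and, in 6.8, exploratory. A point-estimate threshold with an interval for precision is ordinary in that setting. Section 6.3 carries the success heading, 6.10 uses the 75% as a count, and nothing in 13.0 attaches a decision to the interval. At the planning value of 90%, the 6.3 rule passes 98.9% of the time with 20 subjects. All of this stands, and it is why the remedy keeps the threshold instead of replacing it. It does not rescue the claim in 6.6, which states a confidence and a power that the design does not deliver.

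Four stronger readings are tempting, and the documents do not support them:

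- **That 61.7% is a false-positive rate.** A true 75% satisfies the hypothesis in 13.1, so passing there is not an error. The 41.6% at a true 70% shows the rule's leniency below the threshold.
- **That the choice between separate and composite criteria changes the chance of success several-fold.** That holds at 75% under independence. It does not hold at 90%, and the gap vanishes if the same subjects meet both.
- **That 13.0 supports the composite reading.** Its first paragraph is a different, stricter definition, and its bullets give separate criteria. The composite rests on the wording of 6.3 alone.
- **That the single nostril cohort is exempt from the 75% criterion.** Section 13.0 gives it a safety and dose purpose, but states no exemption.

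**Conclusion.** The point holds: the confidence and power stated in 6.6 are not properties of this study as it will be judged and analysed. With 20 subjects, the written rule passes 41.6%, 61.7% and 98.9% of the time at 70%, 75% and 90%. An exact 90% lower-limit rule would have power of 67.7% (one-sided) or 39.2% (two-sided). With 10 subjects the mismatch is larger under a limit rule.

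These figures assume independent subjects with a common success rate and every subject in the group evaluable. They also take 6.3 as a rule on the observed proportion; 6.3 does not use that word, but its phrasing and the count in 6.10 point that way. The calculation in 6.6 is not itself wrong. What is missing is the link between it, the rule and the groups.

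The role of the interval and the differing success definitions are a second, smaller matter of clarification. Most sections already favour two separate criteria, and the size of any difference between readings cannot be fixed from the documents. The whole is worth correcting, but it does not call the feasibility design into question.

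**What to change.** - **6.6:** remove the 90% confidence and 80% power as a property of the study, or replace them with the single-criterion pass probabilities of the 6.3 rule at n = 20 (and at n = 10 if the criterion applies there). Leave the joint figures out of the protocol, because they rest on equal rates and independence.
- **6.3, 13.0 and the summary:** state that an observed proportion of at least 75% is a descriptive feasibility threshold applied to each criterion separately, and that the exact two-sided 90% interval is reported for precision and does not determine success.
- **Definitions:** align 6.3 and the first two paragraphs of 13.0 to that wording, reconciling the whole-duration requirement and the 37 °C starting point with the statements elsewhere.
- **Populations:** keep those already given (summary: maintenance among subjects normothermic by 4 hours who continue cooling; 13.0: treatment initiated and treatment completed). The sponsor should say which governs, and whether the 75% criterion applies to the 10 single nostril subjects.

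The cost is wording, plus the FDA approval that 14.15 requires before an amendment takes effect. No subjects, data or procedures are added. The study gives up its stated confidence and power. The documents do not give enrolment status; if subjects have already been treated, record the date of the clarification and what data had been seen. A confirmatory lower-limit rule would be a separate decision for the sponsor.
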